12.6.2. Liver Safety Study Treatment Restart Guidelines

Restart Following Transient Resolving Liver Stopping Events Not Related to Study Treatment

Restart refers to resuming study treatment following liver stopping events in which there is a clear underlying cause (other than DILI) of the liver event (e.g., biliary obstruction, pancreatic events, hypotension, acute viral hepatitis). Furthermore, restart is not permitted following liver stopping event when the underlying cause was alcoholic hepatitis.

Approval by GSK for study treatment restart can be considered where:

- Investigator requests consideration for study treatment restart if liver chemistries have a clear underlying cause (e.g., biliary obstruction, hypotension and liver chemistries have improved to normal or are within 1.5 x baseline and ALT <3xULN).
- Possible study treatment-induced liver injury has been excluded by the investigator and the study team. This includes the absence of markers of hypersensitivity (otherwise unexplained fever, rash, eosinophilia). Where a study treatment has a confirmed genetic marker associated with liver injury, the presence of the marker should be excluded. If study treatment-related liver injury cannot be excluded, the guidance on study treatment restart in Section 8.1.3 will apply.
- There is no evidence of alcoholic hepatitis.
- IRB/IEC approval of study treatment restart has been obtained.

If restart of study treatment is approved by GSK in writing:

- The participant must be provided with a clear description of the possible benefits and risks of study treatment administration including the possibility of recurrent, more severe liver injury or death.
- The participant must also provide signed informed consent specifically for the restart of study treatment. Documentation of informed consent must be recorded in the study file.
- Study treatment must be administered at the dose specified by GSK
- Participants approved by GSK for restart of study treatment must return to the clinic twice a week for liver function tests until stable liver function tests have been demonstrated and then standard laboratory monitoring may resume as per protocol.
- If the participant meets protocol-defined liver function stopping criteria after study treatment restart, study treatment should be permanently discontinued.

- GSK Medical Monitor, and the IRB/IEC, must be informed of the outcome for the participant following study treatment restart.
- GSK must be notified of any adverse events, as per [Appendix 3](#).

12.7. Appendix 7: Stratification by Region - Region Groupings

Region	Countries ¹
1	
 • Republic of Korea
2	
 • Poland • Russian Federation
3	
 • Australia • France • Germany • Spain
4	
 • Argentina • Brazil
5	
 • US

1. Countries that do not participate or do not randomize any participants will be removed from the regional grouping. If any additional countries are added during the course of the study, they will be added to the regional grouping consistent with study 200807, and such changes will be detailed in the RAP.

12.8. Appendix 8: Country-specific requirements

12.8.1. French Administrative Considerations and Specifics Requirements

This appendix includes all the requirements of the French law (n° 2004-806 of 9th August 2004), and identifies, item per item, the mandatory modifications or additional information to the study protocol and includes specific GSK requirements.

1. Concerning the « STUDY POPULATION»

In line with the local regulatory requirements, the following text in section «**OTHER STUDY ELIGIBILITY CRITERIA CONSIDERATIONS** » is added: A participant will be eligible for inclusion in this study if he /she is either affiliated to or beneficiary of a social security category.

It is the investigator's responsibility to ensure and to document (in source document - patient notes) that the patient is either affiliated to or beneficiary of a social security category.

2. Concerning the “DATA ANALYSIS AND STATISTICAL CONSIDERATIONS” and specially in the “SAMPLE SIZE ASSUMPTION”

The expected number of patients to be recruited in France is declared to the French regulatory authority.

3. Concerning the “STUDY CONDUCT CONSIDERATIONS”

In section “Regulatory and Ethical Considerations, Including the Informed Consent Process”

Concerning **the process for informing the patient** or his/her legally authorized representative, the following text is added:

French Patient Informed Consent form is a document which summarizes the main features of the study and allows collection of the patient's written consent in duplicate. It also contains a reference to the authorization of L'Agence nationale de sécurité du médicament et des produits de santé (ANSM) and the approval from the French Ethics committee.

Concerning **the management of the Patient Informed Consent forms**, the following text is added:

The first copy of the Patient Informed Consent form is kept by the investigator. The second is given to the patient or his/her legally authorized representative

- In section concerning the “**NOTIFICATION TO THE HOSPITAL DIRECTOR**” the following text is added:

In accordance with Article L1123-13 of the Public Health Code, the Hospital Director is informed of the commitment to the trial in his establishment. The

Hospital Director is supplied with the protocol and any information needed for the financial disposition, the name of the investigator(s), the number of sites involved in his establishment and the estimated time schedule of the trial (R.1123-63).

- In section concerning the “**INFORMATION TO THE HOSPITAL PHARMACIST**” the following text is added:

In accordance with Article R.1123-64 of the Public Health Code, the Hospital Pharmacist is informed of the commitment to the trial in his establishment. The Pharmacist is supplied with a copy of the protocol (which allows him to dispense the drug(s) of the trial according to the trial methodology), all information concerning the product(s) of the trial (e.g. included in the CIB), the name of the investigator(s), the number of sites involved in his establishment and the estimated time schedule of the trial.

- In section “**DATA MANAGEMENT**” the following text is added:

Within the framework of this clinical trial, data regarding the identity of the investigators and/or co-investigators and/or the pharmacist if applicable, involved in this clinical trial, and data regarding the patients recruited in this clinical trial (patient number, treatment number, patient status with respect to the clinical trial, dates of visit, medical data) will be collected and computerized in GSK data bases by GlaxoSmithKline Laboratory or on its behalf, for reasons of follow up, clinical trial management and using the results of said clinical trial. According to the Act n° 78-17 of 6th January 1978 further modified, each of these people aforesaid has a right of access, correction and opposition on their own data through GlaxoSmithKline Laboratory (Clinical Operations Department).

4. Monitoring visits

The Health Institution and the Investigator agree to receive on a regular basis a Clinical Research Assistant of GLAXOSMITHKLINE or of a service provider designated by GLAXOSMITHKLINE. The Health Institution and the Investigator agree to be available for any phone call and to systematically answer to all correspondence regarding the Study from GLAXOSMITHKLINE or from a service provider designated by GLAXOSMITHKLINE. In addition, the Health Institution and the Investigator agree that the CRA or the service provider designated by GLAXOSMITHKLINE have direct access to all the data concerning the Study (test results, medical record, etc.). This consultation of the information by GLAXOSMITHKLINE is required to validate the data registered in the eCRF, in particular by comparing them directly to the source data. In accordance with the legal and regulatory requirements, the strictest confidentiality will be respected.

5. Data entry into the eCRF

The Health Institution and the Investigator agree to meet deadlines, terms and conditions of the study's eCRF use here below:

The Health Institution and the Investigator undertake:

- 1) That the Investigator and the staff of the investigator center make themselves available to attend the training concerning the computer system dedicated to the

eCRF of the Study provided by GLAXOSMITHKLINE or by a company designated by GLAXOSMITHKLINE.

- 2) That the Investigator and the staff of the investigator center use the IT Equipment loaned and/or the access codes only for the purpose of which they are intended and for which they have been entrusted to them, namely for the Study achievement, to the exclusion of any other use.
- 3) That the Investigator and the staff of the investigator center use the IT Equipment loaned according to the specifications and manufacturer's recommendations which will have been provided by GLAXOSMITHKLINE.
- 4) To keep the IT Equipment and/or access codes in a safe and secure place and to only authorize the use of this IT Equipment by investigator center staff designated by the principal investigator to enter the data of the Study.
- 5) That the Investigator and the staff of the investigator center enter the data of the eCRF related to a patient visit in the 3 days following the date of the patient visit or, for the patient test results, in the 3 days following the reception of the results of such tests.
- 6) That the Investigator resolves and returns to GLAXOSMITHKLINE the data queries issued by GLAXOSMITHKLINE or a service provider designated by GLAXOSMITHKLINE within 7 days after the reception of the request of clarification or in a period of one (1) day during the final stage of clarification of the data base or in such other period as provided by GLAXOSMITHKLINE and/or a company designated by GLAXOSMITHKLINE.
- 7) To be responsible for the installation and payment of the required Internet connections needed for the use of the IT Equipment, Computer systems and/or access codes.
- 8) To return at the end of the Study the IT Equipment and/or access codes to GLAXOSMITHKLINE or to any company designated by GLAXOSMITHKLINE and any training material and documentation. The IT Equipment cannot under any circumstances be kept by the Health Institution or the Investigator for any reason whatsoever.

6. CTR publication

It is expressly specified that GLAXOSMITHKLINE and/or the Sponsor can make available to the public the results of the Study by the posting of the said results on a website of the GLAXOSMITHKLINE GROUP named Clinical Trial Register (CTR) including the registration of all the clinical trials conduct by the GLAXOSMITHKLINE Group and this before or after the publication of such results by any other process.

7. Data Protection French Law of 6 January 1978 (CNIL)

In accordance with the Data Protection French Law of 6 January 1978 as modified, computer files used by GLAXOSMITHKLINE to monitor and follow the implementation and the progress of the Study are declared with the Commission Nationale de l'Informatique et des Libertés (CNIL) by GLAXOSMITHKLINE. The Investigator has regarding the processing data related to him a right of access, of rectification and of

opposition with GLAXOSMITHKLINE in accordance with the legal provisions. This information can be transferred or be accessed to other entities of GLAXOSMITHKLINE Group in France, Britain or United States, what the Investigator agrees by the signature of the present Protocol.

12.8.2. Country-Specific Requirements for Korea

The following information pertains to all sites in Korea.

Inclusion Criteria – Age Range

In Korea, an adult is considered to be any individual who is ≥ 19 years old.

In regards to Inclusion Criterion #1, in Korea per local laws, only adult participants, who are between 19 and 99 years of age, inclusive, at the time of signing the informed consent will be eligible for inclusion in this study.

Clinical Laboratory Assessments – Point-of-Care Hemoglobin Analyzer

The following point-of-care HemoCue hemoglobin analyzer, or similar device, will be supplied to each study site. Any changes to the details of the device listed below will be provided in the SRM, and will not constitute a protocol amendment.

- Name of device: HemoCue Hb201+ hemoglobin analyzer
- Model number: 121704
- Manufacturer: HemoCue AB: SE-262 23 Angelholm, Sweden

**CONFIDENTIAL**

204837

## 1. INTRODUCTION

The purpose of this reporting and analysis plan (RAP) is to describe the analyses to be included in the Clinical Study Report for Protocol: 204837 (GSK Document Number 2016N279035\_00)

## 2. SUMMARY OF KEY PROTOCOL INFORMATION

### 2.1. Changes to the Protocol Defined Statistical Analysis Plan

Changes from the originally planned statistical analysis specified in the protocol are outlined in [Table 1](#).

**Table 1 Changes to Protocol Defined Analysis Plan**

Protocol	Reporting & Analysis Plan	
Statistical Analysis Plan	Statistical Analysis Plan	Rationale for Changes

 
None
 
	
 
New displays related to COVID-19 pandemic have been added
 
	
 
Assessing the impact of the COVID-19 pandemic
 

 
Only include randomized subjects who have both baseline and at least one Hgb assessment during the EP in the primary Hgb analysis
 
	
 
All randomized subjects will be included in the primary Hgb analysis by imputing missing post-baseline Hgb data using pre-specified multiple imputation approach
 
	
 
Addressing the feedback from FDA
 

 
None
 
	
 
Worsening of Hypertension has been added to the list of AESI and is included in the summary and analysis of AESI
 
	
 
Worsening of Hypertension added to the listing of AESI across the daprodustat program following review of data supporting Japan NDA
 

 
None
 
	
 
Number of RBC transfusions, whole blood transfusions, and transfusion events are included in the exploratory efficacy analysis of RBC and Whole Blood Transfusions
 
	
 
Number of RBC transfusions, whole blood transfusions, and transfusion events have been defined and included in the exploratory endpoints
 

 
None
 
	
 
Time to first RBC transfusion and/or whole blood transfusion is included in the exploratory efficacy analysis of RBC and Whole Blood Transfusions
 
	
 
Time to first RBC transfusion and/or whole blood transfusion has been included in the exploratory endpoints
 

 
Subgroup: Weight: < 75kg, ≥75kg
 
	
 
Baseline post-dialysis weight quartiles
 
	
 
Subgroup update prior to unblinding the trial
 


 
Baseline hsCRP: ≤3 mg/L, >3 mg/L
 
	
 
Baseline hsCRP quartiles
 
	
 
Subgroup update prior to unblinding the trial
 

CONFIDENTIAL

204837

Protocol	Reporting & Analysis Plan	
Statistical Analysis Plan	Statistical Analysis Plan	Rationale for Changes

 
PK endpoint: pre-dose trough (Ctau)
 
	
 
“Pre-dose trough (Ctau)” has been replaced with “Pre-dose trough (Ctrough)”
 
	
 
Ctrough is more accurate for TIW dosing regimen
 

 
None
 
	
 
New PK-related parameters (Dapro Efficacy Dose Parameters, Dapro Efficacy Special Parameters, Dapro Safety Dose Parameters, Dapro Safety Special Parameters)
 
	
 
Provides transparency to the intermediate endpoints required for figure creation at individual and population level.
 

 
Explore the graphical relationship between Dapro exposure and Mean Hgb
 
	
 
Explore the graphical relationship between Dapro exposure and Mean Hgb change from baseline
 
	
 
Mean Hgb change from baseline is a better assessment of daprodustat efficacy than absolute Hgb.
 

## 2.2. Study Objective(s) and Endpoint(s)

Objectives	Endpoints
Primary Objectives	Primary Endpoints

 
To compare the effect of daprodustat to epoetin alfa on Hgb efficacy when administered three-times weekly to hemodialysis-dependent participants (non-inferiority)
 
	
 
Mean change in Hgb between baseline and over the evaluation period (EP, mean over Weeks 28 to 52)
 

Principal Secondary Objectives	Principal Secondary Endpoints (tested for superiority, adjusted for multiplicity)

 
To compare daprodustat administered three-times weekly to epoetin alfa on the use of intravenous (IV) iron
 
	
 
Average monthly IV iron dose (mg)/participant to Week 52
 

Safety Objectives	Safety Endpoints

 
To compare the safety and tolerability of daprodustat administered three-times weekly to epoetin alfa
 
	
 
Incidence and severity of AEs and serious adverse events (SAEs) including AEs of special interest and MACE
 
Reasons for discontinuation of study treatment
 
Absolute values and changes from baseline in laboratory parameters, BP and heart rate (HR)
 

Secondary Objectives	Secondary Endpoints (Non-PK endpoints tested for superiority  , with no multiplicity adjustment)

 
To compare the effect of daprodustat administered three-times weekly to epoetin alfa on Hgb variability
 
	
 
Hgb change from baseline to Week 52
 
% time Hgb in analysis range (10 to 11.5 g/dL) during the EP
 
N (%) responders, defined as mean Hgb within the Hgb analysis range 10 to 11.5 g/dL during the EP
 

 
To compare daprodustat administered three-times weekly to epoetin alfa on the time to rescue
 
	
 
Time to stopping study treatment due to meeting rescue criteria
 

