### 5.4. Examination of Covariates, Other Strata and Subgroups

#### 5.4.1. Covariates and Other Strata

The list of covariates and other strata may be used in descriptive summaries and statistical analyses, some of which may also be used for subgroup analyses. Additional covariates and other strata of clinical interest may also be considered.

Category	Details
Strata	Regions listed in Section 5.3.
Covariates	Baseline Hgb (For the analysis of the primary endpoint and other analyses of Hgb-related endpoints)  For subgroup analyses, statistical models will be adjusted for the covariates used in the original analysis (randomization stratification factor and baseline hemoglobin), subgroup, treatment and treatment by subgroup interaction (see Section 5.4.2 for the subgroup variables.).

Randomization is stratified by the prognostic factor, region, which will be taken into account within the analysis models.

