
 
For the secondary analysis of Hgb change from baseline to Week 52, a mixed model repeated measures (MMRM) approach will be used with an unstructured covariance matrix to compare the difference in means between arms. The model will be fitted to Hgb data collected after baseline up to Week 52, excluding values collected during the stabilization period (Day 1 to Week 28). The model will include factors for treatment, time, prognostic randomization stratification factor (region, see Section 5.3), baseline Hgb and the baseline Hgb by time and treatment by time interaction terms. Analyses will be done with the MIXED procedure in SAS, using the Kenward-Roger option to estimate denominator degrees of freedom and standard errors. This analysis will be performed using all available Hgb values (on and off-treatment) and separately using evaluable Hgb values only (see Section 14.6.3). In the analysis using all available Hgb values, subjects who withdraw from the study before Week 52 are considered to be missing at random and in the analysis using evaluable Hgb values, subjects who permanently discontinue study treatment before Week 52 are assumed to be missing at random.
 
For the analysis of % time in range, the method by Rosendaal [Rosendaal, 1993] will be used to calculate the percentage of time (days) a subject's Hgb is below, within and above the Hgb analysis range of 10 to 11.5 g/dL during the EP (Weeks 28-52). A van Elteren test (stratified Wilcoxon rank sum test) will be used to compare the percentage of time in range between treatment arms, adjusting for treatment and the prognostic randomization stratification factor (see Section 5.3). This analysis will be performed using evaluable Hgb
 

values only. Hodges-Lehmann estimate of the treatment difference will be used to assess non-inferiority in % time in range.
 
 
For the Hgb responder analysis, mean Hgb during the EP will be defined as in the while on-treatment evaluable Hgb supportive analysis (Section 14.6.3). Responders will be subjects with a mean Hgb during the EP that falls within the Hgb analysis range of 10-11.5 g/dL. A Cochran-Mantel-Haenszel (CMH) chi-squared test, adjusting for treatment and the prognostic randomization stratification factor (region as randomized, see Section 5.3), will be used to compare the number and % of responders between the treatment groups.
 

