
 
Subgroup analyses will be performed for all Hgb variability endpoints, using the region and hyporesponder subgroups only (described in Section 5.3 & Section 5.4), in a method similar to that described for the subgroup analyses of the primary and principal secondary analyses
 

CONFIDENTIAL

204837

*Time to Rescue*

Secondary Efficacy Statistical Analyses: Time to Rescue
Endpoint / Variables

 
Time to stopping study treatment due to meeting rescue criteria
 

Model Specification

 
The Cox Proportional Hazards model will adjust for the following baseline categorical values: 
 
Treatment
 
Region (as randomized, see Section 5.3 & Section 5.4.1)
 
 
 
Confidence intervals for the rate per 100 person-years will also be reported. For within-group rates, the two-sided 95% CI will be obtained using an exact Poisson method. For difference in rates between treatments, the two-sided 95% CI will be constructed with a Normal approximation using Wald's method [Liu, 2006].
 
Analysis will include only those efficacy endpoints occurring within the time period for treatment discontinuation. Calculation of time-to-event or censoring is described in further detail in Section 14.6.3.
 
Time to stopping study medication due to meeting rescue criteria is defined as the time from Randomization until the date on which a subject permanently stops study medication due to meeting criteria for rescue.
 

Model Results Presentation

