
 
Summaries will include (see Section 14.6.3): 
 
the number and percentage of subjects meeting evaluation criteria for rescue and the number of occurrences (events),
 
the number and percentage of subjects unable to be evaluated for rescue, and
 
the number and percentage of subjects meeting rescue.
 
 
 
The analysis model results presentation: 
 
Number (%) of subject permanently stopping study treatment due to meeting rescue criteria within each treatment arm
 
Number (%) of subject censored
 
Incidence rate per 100 person-year and the associated two-sided 95% confidence intervals for each treatment arm
 
Hazard ratio and the associated two-sided 95% confidence interval
 
One-sided p-value for the test of superiority of daprodustat vs rhEPO
 
Absolute rate difference per 100 person-year and the associated two-sided 95% confidence interval
 
 
 
A Kaplan-Meier plot of time to stopping study treatment due to meeting rescue criteria will be produced.
 

Model Results Interpretation

 
One-sided p-values will be compared to 0.025 to assess nominal significance
 

Subgroup Analyses

 
Subgroup analyses will be performed for the time to rescue endpoint using the hyporesponder subgroup only (described in Section 5.4). Cox Proportional Hazards model will be adjusted for the covariates used in the original analysis (region, treatment), hyporesponder subgroup, and treatment by subgroup interaction.
 

CONFIDENTIAL

204837

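### The time-to-rescue Cox model and the responder test adjust for region only, although SAP 5.4.1 lists baseline Hgb for Hgb-related endpoints: valid, but slightly less efficient than a free alternative

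*SAP*

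**What the plan says.** SAP 5.4.1 names one covariate: "Baseline Hgb (For the analysis of the primary endpoint and other analyses of Hgb-related endpoints". The sentence introducing that table is permissive: the listed covariates are available for use, not required.

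SAP 7.3.1 then specifies each secondary model.

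- **Time to rescue.** SAP 2.2 lists the endpoint as "Time to stopping study treatment due to meeting rescue criteria". Its model in 7.3.1 reads "The Cox Proportional Hazards model will adjust for the following baseline categorical values": treatment, and "Region (as randomized, see Section 5.3" and 5.4.1). There is no other term. The hyporesponder subgroup model confirms this by describing the "covariates used in the original analysis (region, treatment").
- **Responders.** "Responders will be subjects with a mean Hgb during the EP that falls within the Hgb analysis range of 10-11.5 g/dL". The comparison is a CMH test "adjusting for treatment and the prognostic randomization stratification factor (region as randomized, see Section 5.3").
- **Week 52 Hgb change.** In the same section, this mixed model does include baseline Hgb and its interaction with time.

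Protocol 7.9 (Table 8) defines rescue. Evaluation starts when HemoCue Hgb remains below 9 g/dL despite dose increases, or is below 7.5 g/dL despite an increase at the prior visit. Treatment stops if Hgb is still below 9 g/dL about 4 weeks after the initial intervention, or if more than two units of packed red cells were needed outside acute bleeding. Protocol 6.1 admits Day 1 Hgb from 8 to 11.5 g/dL. Randomization is stratified by region only (protocol 7.3).

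**The concern.** Both endpoints are functions of later Hgb. The responder endpoint sits under the Hgb variability objective. Rescue has its own objective, but its main route is a Hgb threshold. Protocol 5.5 reports that baseline Hgb and prior rhEPO dose were among the most relevant covariates of Hgb response in the sponsor's own modelling. A participant who starts lower has less distance to fall, so Day 1 Hgb can reasonably be expected to predict rescue. It is measured in everyone and is already a term in the primary model.

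With 268 versus 134 participants and probably few rescue events, a chance difference in Day 1 Hgb could move the hazard ratio and invite an unplanned adjusted analysis after unblinding. Pre-specifying the term avoids that argument.

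There is also an inconsistency for the programmer. SAP 5.4.1 says subgroup models carry the covariates of the original analysis and names these as the stratification factor and baseline Hgb. The rescue subgroup model in 7.3.1 carries region and treatment only, and a region-stratified CMH test has no place for a continuous covariate.

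**Working it through.** **What the plan quantifies.** There is no event count, rate or power for rescue or responders. The only power figure is for the primary endpoint, and it reproduces. With 240 and 120 evaluable, SE = 1.5 × √(1/240 + 1/120) = 0.168; half-width 1.96 × 0.168 = 0.33; largest passing difference -0.75 + 0.33 = -0.42; power Φ(0.75/0.168 - 1.96) = 99.4%, against the stated >90%. This point contests none of that.

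**Chance imbalance, by hand.** Assume a baseline Hgb SD of 0.8 g/dL. The SD of the between-arm difference in mean Day 1 Hgb is 0.8 × √(1/268 + 1/134) = 0.8 × 0.106 = 0.085 g/dL. Multiplying by the assumed log hazard ratio per 1 g/dL gives the 1 SD shift in the treatment log HR:

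- 1.5-fold: 0.085 × 0.405 = 0.034, about 3%
- 2-fold: 0.085 × 0.693 = 0.059, about 6%
- 3-fold: 0.085 × 1.099 = 0.093, about 10%

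Simulated fits differ somewhat more, about 5% to 13% over this range and about 8% at 2-fold, because with few events the two fits also diverge through which participants happen to supply them.

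**Scale of that shift.** With HR 0.5 and 2:1 allocation, events split about equally, so SE(log HR) ≈ 2/√events: 0.43 with 22 events and 0.35 with 33. A shift of 8% is 0.077 on the log scale, or 0.18 to 0.22 of an SE. A shift of 13% is 0.122, or 0.28 to 0.35 of an SE.

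**Power for rescue, simulated.** Assumptions: 402 participants, 2:1; five equal regions; baseline Hgb drawn from a normal distribution (mean 10.3, SD 0.8) truncated to 8 to 11.5; about 22% other discontinuation over the year; true HR 0.5; one-sided 2.5%; 700 runs.

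| Control 1-year rescue | Hazard ratio per 1 g/dL lower Hgb | Mean events | Power, region only | Power, plus Hgb | HR, region only | HR, plus Hgb |
|---|---|---|---|---|---|---|
| 4% | 1.5 | 11.8 | 22% | 20% | 0.48 | 0.47 |
| 4% | 2.5 | 13.8 | 25% | 24% | 0.54 | 0.53 |
| 10% | 1.5 | 26.1 | 43% | 43% | 0.50 | 0.49 |
| 10% | 2.5 | 31.4 | 47% | 50% | 0.51 | 0.49 |
| 20% | 1.5 | 52.3 | 69% | 71% | 0.50 | 0.50 |
| 20% | 2.5 | 61.6 | 74% | 77% | 0.52 | 0.50 |

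Monte Carlo error is about √(0.25/700) = 1.9 points. The 4% rows are rough: in the four scenarios at that rate (these two and their null counterparts), 358 to 623 of 700 runs gave a usable fit. With no treatment effect, rejection was 2.0% to 3.3% without and 2.0% to 3.7% with baseline Hgb. Two further simulations agree. At 2-fold per g/dL, power moved from 32% to 35% (22 events) and from 45% to 46% (33 events). Over 19 to 49 events the change was about -1 to +4.5 points.

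**Power for responders, simulated.** With 360 evaluable and response rates of about 62% and 53%, CMH was compared with logistic regression on region, baseline Hgb and its square. For baseline-to-EP correlations of 0, 0.2 and 0.4, power was 39% v 38%, 39% v 39% and 34% v 35%. Two-sided type I error was about 5% for both.

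**The case against.** The strongest reply is that nothing here is an error. SAP 5.4.1 is permissive and 7.3.1 then states each model. Time to rescue is listed under its own objective, so calling it Hgb-related is an inference from the trigger. The pattern also looks deliberate: analyses of change in a continuous measure take the baseline value, while rank, categorical and event analyses use the stratum alone. The van Elteren test for time in range, the BP-exacerbation rate model and the time-to-transfusion model all follow it. Both tests are nominal, outside the testing hierarchy, and exploratory under protocol 10.3.1. The planned hyporesponder subgroup model already brings in some of the same information, since the resistance index behind it divides prior ESA dose by dry weight and Day 1 Hgb. All of this stands.

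A reader might infer more than the documents support:

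- **That the region-only tests are biased.** They are not. Randomization protects them, and chance imbalance is already reflected in the confidence interval.
- **That the SAP breaks its own rule.** A permissive list cannot be broken; the mismatch is unexplained, not a breach.
- **That entering below 9 g/dL leads directly to rescue.** Failed dose increases, an intervention and a recheck come first, and transfusion is a separate route.
- **That adjustment is costless.** Going from five to six parameters (treatment, four region terms, Hgb) with 22 events means 22/5 = 4.4 falling to 22/6 = 3.7 events per parameter.

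**Conclusion.** The point holds as a minor improvement. The rescue Cox model and the responder test omit a covariate that the SAP lists for this kind of endpoint, that its Week 52 model uses, and that the sponsor's modelling found relevant.

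For rescue the gain is about 0 to 4 power points, and nothing detectable at around 20 events or fewer. The region-only HR is closer to 1 by at most about 0.02; part of that is the usual difference between a marginal and a conditional hazard ratio, not error. The more practical benefit is settling in advance how a chance imbalance worth 5% to 13% of the HR (1 SD) is handled. For responders, the change of -1 to +1.5 points is within simulation noise, so the documents give no ground for saying that the CMH test loses meaningful power or should be replaced.

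These sizes rest on assumed rescue rates, prognostic strength and baseline SD; none is in the documents. A stronger predictor with more events would raise the gain, and a weak one would remove it. Adding prior ESA dose as well is debatable and is not needed for this point.

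**What to change.** Before unblinding:

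1. In SAP 7.3.1, Time to Rescue, add Day 1 Hgb as a continuous term, using the same baseline value as the primary model. Make the same change in the hyporesponder subgroup model.
2. Keep the region-only Cox model as a pre-specified supportive analysis. Do not make it a fallback chosen according to the number of events, since that would let the data choose the model.
3. For responders, keep the region-stratified CMH test. Add a supportive logistic model with treatment, region and baseline Hgb, allowing a non-linear Hgb term because 10 to 11.5 g/dL is a two-sided target.
4. State in SAP 5.4.1 which Hgb-related analyses use region only. The van Elteren test would be one.

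The cost is a few lines of SAP text and two extra model outputs, with no new data or derivations. The one real downside is the additional Cox parameter if rescue events turn out to be few.
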